Title: Comparison of Bolus and Continuous Hydration Regimens for the Prevention of Contrast-Associated Acute Kidney Injury in the Emergency Department: A Randomized Controlled Non-Inferiority Trial

Document Date: 2024-08-07

Comparison of Bolus and Continuous Hydration Regimens for the Prevention of Contrast-Associated Acute Kidney Injury in the Emergency Department: A Randomized Controlled Non-Inferiority Trial

[name], [name], [name], [name],
[name]

Study Protocol

Study Design and Settings

A single-center, prospective, open-label, non-inferiority randomized controlled clinical trial was conducted at the ED of a tertiary hospital. The ED staff consisted of a mix of emergency medicine specialists, emergency medicine residents, and general practitioners. The ED admits all trauma patients regardless of age, as well as non-trauma patients aged 18 years and older. An average of 385000 patients are admitted annually, and imaging with contrast media is performed on an average of 12250 patients.

The study was approved by the Clinical Research Ethics Committee of xxx (Decision No: E-66291034-202.3.02-4819, Date: 07/08/2024) and was conducted in accordance with the principles of the Helsinki Declaration. This study has been reported in accordance with the CONSORT statement. Informed written consent was obtained from all patients participating in the study.

Study Enrollment

Between August 10, 2024, and March 26, 2025, patients aged 18 and over who presented to the ED with creatinine levels above the reference range (1.2 mg/dl in men and 1.1 mg/dl in women) and underwent contrast-enhanced tomography were deemed eligible for inclusion in the study. Exclusion criteria were as follows: (1) Pregnancy, (2) known allergy history to contrast agents, (3) exposure to contrast agents within the last 72 hours, (4) being on dialysis due to end-stage kidney disease, (5) presenting with decompensated heart failure, (6) patients who were unable to provide informed consent.

Eligible patients were randomly allocated in a 1:1 ratio to receive either bolus hydration or continuous hydration therapy. Permuted block randomization was employed at each

participating site to distribute patients, stratified by age groups (18–44, 45–59, 60–74, and 75 years and older) and gender. This study did not use blinding. Both the implementers of the intervention and the researchers evaluating the outcome measures are aware of the intervention groups.

Interventions

After the patients were divided into two groups, one group received bolus hydration therapy while the other group received continuous hydration therapy.

In the Bolus hydration therapy group, 500 ml of 0.9% saline treatment was started half an hour before the procedure and after the procedure, 1000 ml of 0.9% saline treatment was continued at a rate of 500 ml/h to be completed in 2 hours. A total of 1500 ml 0.9% saline hydration therapy was administered over 2.5 hours.

In the Continuous hydration therapy group, saline treatment started 2 hours before the intravenous (IV) contrast agent application at a rate of 150 ml/h, and hydration was applied for 8 more hours after the procedure at the same rate. A total of 1500 ml 0.9% saline hydration therapy was administered over 10 hours.

According to the literature, individuals with an ejection fraction of less than 40% got a half-dose hydration protocol^{12,13}. In the bolus hydration group, 250 ml of treatment was administered half an hour before the procedure, and hydration was continued at a rate of 250 ml/h for 2 hours after the procedure. In the continuous hydration group, 75 ml/h of hydration was administered for 2 hours before the procedure and for 8 hours after the procedure.

The IV contrast agent used in the study was iohexol, which belongs to the non-ionic low osmolar contrast agent group. 300 mgI/ml 100 ml solutions were used, and the dose was adjusted between 80 and 100 ml depending on the imaging and the patient. In the majority of patients, 100 ml of contrast was administered, with an average of 98 ml of solution given in the bolus hydration group and an average of 96 ml of solution given in the continuous hydration group.

Patients were given control forms to provide follow-up blood samples 48–72 hours later and were asked to present to the ED with the form on the specified date. To inquire about the development of dialysis needs and mortality status, patients were contacted 30 days later to gather information.

Outcomes

The primary outcome of our study was the development of CA-AKI, defined as an increase in serum creatinine value by $\geq 25\%$ compared to baseline or an absolute increase in serum creatinine value by ≥ 0.5 mg/dL within 48-72 hours after contrast administration.

The secondary outcomes of the study are the need for dialysis and all-cause mortality within 30 days.

Statistical Analysis

Categorical variables are presented as frequencies and percentages. Continuous variables were assessed for normality using the Kolmogorov-Smirnov and Shapiro-Wilk tests; non-normally distributed variables are reported as median (25th–75th percentiles). Between-group comparisons of categorical variables were performed using Pearson's Chi-square or Fisher's Exact test, as appropriate. Continuous variables were compared using the Mann-Whitney U test for independent groups and the Wilcoxon signed-rank test for paired groups. The incidence of contrast-associated acute kidney injury (CA-AKI) between hydration protocols was compared using risk differences (RDs) with 95% confidence intervals (CIs). Non-inferiority of the bolus hydration protocol was assessed using a pre-specified margin; the protocol was considered non-inferior if the upper bound of the 95% CI was below this margin. All other statistical tests were two-sided, and statistical significance was set at $p < 0.05$. Analyses were conducted using IBM SPSS Statistics.

Power Calculation

The sample size calculation aims to establish the non-inferiority of bolus prophylaxis relative to routine prophylaxis concerning the primary outcome, CA-AKI. The anticipated incidence of CA-AKI patients following conventional prophylaxis is 6.2%⁶, while the non-inferiority margin, derived from clinical consensus and literature, is 8%¹⁴. A one-tailed hypothesis was established, with a Type I error rate (α) of 0.05 and a statistical power ($1-\beta$) of 0.80. In light of clinical settings, the dropout rate was established at 15%, resulting in a total inclusion of 266 individuals, with 133 assigned to the regular prophylaxis group and 133 to the bolus prophylaxis group¹⁵. The computation employed the complimentary website sealedenvelope.com¹⁶.

At conclusion of the study, a total of 257 patients were included into the final analysis. While 113 individuals in the bolus and continuous prophylaxis groups sufficed for the study, a total of 257 patients were recruited, adhering to dropout limitations and ensuring an adequate sample size.

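### Eligibility is worded on a CT that takes place after randomisation, and the single non-inferiority test runs on an unnamed set of 257, so losses after randomisation cannot be seen against the 8-point margin

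*Combined protocol and SAP*

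**What the plan says.** **Eligibility (Study Enrollment).** Adults with creatinine above the reference range who "underwent contrast-enhanced tomography were deemed eligible for inclusion in the study". The next paragraph continues: "Eligible patients were randomly allocated in a 1:1 ratio to receive either bolus hydration or continuous hydration therapy". The same section says there was no blinding: "Both the implementers of the intervention and the researchers evaluating the outcome measures are aware of the intervention groups".

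**Sequence (Interventions).** Hydration follows allocation: "After the patients were divided into two groups, one group received bolus hydration therapy while the other group received continuous hydration therapy". In the bolus arm, "500 ml of 0.9% saline treatment was started half an hour before the procedure". In the continuous arm, "saline treatment started 2 hours before the intravenous (IV) contrast agent application at a rate of 150 ml/h". Patients were asked to come back to the ED for a blood sample at 48–72 h.

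**Outcome (Outcomes).** CA-AKI is a creatinine rise in the 48–72 h after contrast. It therefore needs both a contrast scan and a later sample.

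**Analysis (Statistical Analysis, Power Calculation).** Non-inferiority is judged by the upper limit of the 95% CI for the risk difference, against a margin of 8%. No intention-to-treat, all-randomised, modified or per-protocol set is named, and there is no rule for a patient without a scan or a follow-up creatinine. The plan was 133 per arm, 266 in all, allowing 15% dropout. On numbers achieved, "a total of 257 patients were included into the final analysis"; the following sentence gives the same 257 as the number recruited.

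**The concern.** Two gaps combine.

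First, the eligibility sentence depends on an event that can only happen after randomisation. Followed as written, it turns a patient who was randomised but not scanned into one who was never eligible. Staff knew the allocation, and the regimens require different minimum lead times before the scan, so losses need not be balanced between arms.

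Second, nothing in the analysis text would reveal such losses. The primary outcome can be computed only for patients who were scanned and who returned, so the default is an analysis of completers. The return visit is the better-documented route of loss, because the plan itself allows for 15% dropout.

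A comparison of completers no longer rests on randomisation alone. In a non-inferiority trial the claim depends on one upper bound falling below a fixed limit. Without a second analysis set and counts by arm, a reader cannot tell whether the claim would survive the patients left out.

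**Working it through.** **1. Order of events, with the sections side by side**

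| Step | Study Enrollment | Interventions |
|---|---|---|
| 1 | Contrast CT undergone, so eligible | Allocated to an arm |
| 2 | Randomised | Saline started, 0.5 h or 2 h before the scan |
| 3 | – | Contrast CT |
| 4 | – | Further saline; return sample at 48–72 h |

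Saline that starts after allocation and before the scan puts the CT after randomisation. Having undergone the CT cannot then be a condition for being randomised.

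**2. The plan's own sample size**

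Inputs from Power Calculation: control risk 6.2% (taken as equal in both arms), margin 8 points, one-sided α 0.05, power 0.80, dropout 15%.

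- n per arm = (1.645 + 0.842)² × 2 × 0.062 × 0.938 / 0.08² ≈ 112.4, rounded up to 113.
- 113 / 0.85 = 132.9, rounded up to 133; 2 × 133 = 266.

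Both stated figures reproduce. The sample size is not the problem here.

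**3. What the counts allow**

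- 257 recruited and 257 analysed, taken literally, means no loss at all, in a design that relies on patients coming back to the ED.
- If instead the planned 266 were randomised (an assumption), 266 − 257 = 9 are unaccounted for, which is 9/266 = 3.4%.
- The dropout allowance would have tolerated 266 − 2 × 113 = 40.

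The number randomised and the split of the 257 by arm are not given, so the documents do not settle which of these applies.

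**4. Could nine patients matter?**

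Assumptions, none of them from the documents: 133 randomised per arm; 129 bolus and 128 continuous analysed; 8 events in each arm, close to the planned 6.2%. The nine absent patients are then 4 bolus and 5 continuous. Upper bound = d + 1.96 × √[p_B(1−p_B)/n_B + p_C(1−p_C)/n_C], with d = p_B − p_C.

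| Scenario | Bolus | Continuous | d (points) | SE (points) | 95% upper bound (points) |
|---|---|---|---|---|---|
| Completers only | 8/129 | 8/128 | −0.05 | 3.01 | 5.9 |
| Nine restored, all non-events | 8/133 | 8/133 | 0.00 | 2.92 | 5.7 |
| Two of 4 bolus events, no continuous | 10/133 | 8/133 | 1.50 | 3.08 | 7.5 |
| Three of 4 bolus events, no continuous | 11/133 | 8/133 | 2.26 | 3.16 | 8.4 |
| All 4 bolus events, no continuous | 12/133 | 8/133 | 3.01 | 3.23 | 9.3 |
| No bolus events, all 5 continuous | 8/133 | 13/133 | −3.76 | 3.30 | 2.7 |

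Under these assumptions the conclusion changes once three of the four absent bolus patients have events and none of the five continuous patients do. With 1.645 in place of 1.96, matching the one-sided 0.05 of the sample size, the most adverse row is 8.3 points, still above 8, while the three-event row is 7.4. Counting the missing as non-events lowers the bound from 5.9 to 5.7, so that rule favours non-inferiority.

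**The case against.** **The wording may only be loose tense.** Nearly the whole text is a past-tense report, so the eligibility line may mean patients who were to undergo a CT. That is a fair reading and would make eligibility a proper baseline condition. It would not supply an analysis population, a rule for missing outcomes or the number randomised.

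**The documents do not say the analysed set was defined by the CT.** A reader might infer that it was, and that the arms compared are no longer the randomised ones. The sentence concerns entry to the study; no section defines the analysed set, and no exclusion is shown to have been applied.

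**Arm-dependent loss is not shown.** A reader might infer a wait four times as long in the continuous arm, with more cancelled scans. The text gives only when saline starts relative to the scan, so 2 h and 0.5 h are minimum lead times; time from randomisation to scan is not reported and could be equal. A scan brought forward is still a scan: that patient departs from the regimen but stays eligible.

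**A bias figure built on unscanned patients has little meaning.** One could assign such patients a high CA-AKI risk and calculate a shift, but CA-AKI is undefined without contrast and the documents give no such risk. No estimate of that kind is offered here.

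**The adverse scenario is extreme, and the trial has enrolled.** Both are true. The scenario shows sensitivity and makes no claim about likelihood. Enrolment closed on March 26, 2025, so new wording cannot change who entered or recover samples never taken. Requiring two analyses to agree is one convention among several. The reporting and analysis gap remains, and it can still be closed.

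**Conclusion.** The point holds in a limited form. As written, eligibility rests on an event after randomisation, and the only non-inferiority test is applied to an unnamed set whose size doubles as the number recruited. Followed literally, the text produces a completers analysis with uncounted losses in an open-label trial.

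It does not follow that the result is biased: neither the direction nor the size of any bias can be determined from the documents. If 266 were randomised and nine are absent, with 8 events per arm among those analysed, the 95% upper bound could lie anywhere from 2.7 to 9.3 points depending on those nine, against a completers value of 5.9. If 257 were randomised and all were analysed, there is no loss and the matter reduces to correcting the wording and stating the population. The sponsor should resolve this before claiming non-inferiority.

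**What to change.** 1. **Eligibility.** Word it as contrast-enhanced CT planned, fixed before randomisation, and confirm that this is how patients were enrolled.
2. **Patient flow.** Report by arm the numbers randomised, scanned, completing the allocated regimen and having a 48–72 h creatinine. Reconcile the two uses of 257 with each other and with the planned 266. This fits the protocol's statement that it reports to CONSORT.
3. **Primary outcome.** Analyse all randomised patients as allocated, with a stated rule for patients without a scan or a sample. Add a sensitivity range over the missing outcomes that does not simply count them as non-events. Present a per-protocol analysis (scanned, allocated regimen completed) alongside, and claim non-inferiority only if both upper bounds are below the same margin.
4. **Secondary outcomes.** Analyse dialysis and 30-day mortality in all randomised patients, since neither requires a scan or the return sample.

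**Cost.** One line of wording, a flow table and a few extra analysis runs. The real price is an explicit missing-data assumption, because CA-AKI is undefined in unscanned patients, and possibly a less favourable bound. Samples never taken cannot be recovered, so the sensitivity range has to carry that uncertainty.

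### Outcome evaluators know the arm, with no reason given, although CA-AKI could be classified from laboratory values without it; the fixed creatinine threshold limits the resulting risk but does not remove it.

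*Combined protocol and SAP*

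**What the plan says.** Study Enrollment describes an unblinded trial and extends this to outcome assessment: "Both the implementers of the intervention and the researchers evaluating the outcome measures are aware of the intervention groups". No reason is given, and no masked step is described elsewhere.

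Under Outcomes, the primary endpoint CA-AKI is met by "an increase in serum creatinine value by $\geq 25\%$ compared to baseline" or by "an absolute increase in serum creatinine value by ≥ 0.5 mg/dL within 48-72 hours after contrast administration". The primary sample depends on the patient coming back. Under Interventions: "Patients were given control forms to provide follow-up blood samples 48–72 hours later and were asked to present to the ED".

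The 30-day events are separate: "The secondary outcomes of the study are the need for dialysis and all-cause mortality within 30 days". They are collected by contact: "To inquire about the development of dialysis needs and mortality status, patients were contacted 30 days later to gather information". Whether the caller knows the arm is not stated for that step specifically.

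Under Statistical Analysis, non-inferiority is judged on the CA-AKI risk difference alone, by comparing the upper 95% confidence limit with the margin. Power Calculation gives the margin as 8%, the expected control rate as 6.2% and the number analysed as 257.

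**The concern.** A 2.5-hour and a 10-hour infusion can hardly be concealed at the bedside. That does not explain unmasked evaluation two to three days later, when the primary outcome is a comparison of two laboratory values.

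The assay is objective. The path from assay to event flag is less so, because the documents leave three points open:

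- which pre-contrast creatinine is the baseline, if a patient has more than one;
- which value counts, if there are several within 48-72 h, and what happens to a sample outside the window;
- how patients who do not return are pursued, and how they are handled if no sample is obtained.

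People who know the arm settle each of these. In a non-inferiority trial, missing a bolus event or adding a continuous event moves the result toward success. With few events, a few such choices could matter, and a reader cannot tell from the plan that they were made evenly.

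**Working it through.** **Inputs from the documents.** Control rate 6.2%, margin 8% (read as an absolute risk difference), one-sided α 0.05, power 0.80, dropout 15%, 257 analysed (Power Calculation); 1:1 allocation (Study Enrollment); upper limit of the 95% CI below the margin (Statistical Analysis).

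**Assumptions, because the documents are silent.** Split of 128 bolus and 129 continuous; two-sided 95% interval; Wald or Newcombe method; equal rates in the two arms for planning.

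**1. Reproduce the plan's sample size.** n = (1.645 + 0.842)² × 2 × 0.062 × 0.938 / 0.08² = 112.4, so 113 per arm. Then 113 / 0.85 = 132.9, so 133 per arm and 266 in total. This matches the plan. Masking the classification does not enter the formula, so it leaves N unchanged.

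**2. Weight of one patient.** Expected events are 0.062 × 129 = 8.0 per arm. One reclassified patient moves the risk difference by 1/128 = 0.78 points, about a tenth of the margin.

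**3. Tipping point.** Hold continuous at 8/129 and vary the bolus count out of 128. The Wald upper limit is d + 1.96 × √[p₁(1−p₁)/128 + p₀(1−p₀)/129]. The Newcombe upper limit is d + √[(u₁−p₁)² + (p₀−l₀)²], where u₁ and l₀ are Wilson limits.

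| Bolus events | Wald 95% upper | Newcombe 95% upper |
|---|---|---|
| 8 | 5.96% | 6.41% |
| 9 | 6.91% | 7.36% |
| 10 | 7.85% | 8.31% |
| 11 | 8.79% | 9.24% |

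Wald passes up to 10 events and Newcombe up to 9. From 8 v 8, the verdict therefore flips with 3 (Wald) or 2 (Newcombe) extra bolus events. Exchanging the arm sizes (129 bolus, 128 continuous) does not change this: Newcombe gives 7.24% at 9 and 8.17% at 10, and Wald gives 7.74% at 10 and 8.67% at 11. With a one-sided 5% limit, which matches the sample-size α, 3 (Newcombe) or 4 (Wald) extra events are needed at 128/129.

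**4. Effect on the error rate.** For each continuous count x₀, let m(x₀) be the largest bolus count that still passes. If k bolus events are lost from the count, the probability of declaring non-inferiority is Σ P(x₀) × P(X₁ ≤ m(x₀) + k), with x₀ ~ Bin(129, 0.062) and X₁ ~ Bin(128, p₁). At the margin, p₁ = 0.062 + 0.08 = 0.142.

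| Bolus events lost | Wald 95% | Newcombe 95% |
|---|---|---|
| 0 | 3.0% | 2.5% |
| 1 | 5.1% | 4.2% |
| 2 | 8.2% | 6.8% |

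**5. How often the result would lie near the boundary.** With 6.2% in both arms, the chance that adding or removing at most two bolus events changes the verdict is 36% (Wald) to 39% (Newcombe) with the 95% interval, and 29% to 31% with the one-sided 5% limit. The chance that losing up to two bolus events turns a fail into a pass is 90.3 − 76.0 = 14.3% (Wald) or 86.4 − 69.8 = 16.6% (Newcombe).

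**The case against.** The strongest reply is that CA-AKI is a numeric threshold. The presenting ED creatinine determines eligibility, so it is the natural baseline. The plan describes one return visit on a set date, and mentions neither repeated baselines nor multiple in-window samples. Pursuing non-returners is follow-up rather than scoring. On this view the real gap is unstated definitions, which would exist even with masked assessors. Much of this stands: the threshold does limit discretion. But the baseline rule is still not written down, and it is where rules are missing that knowledge of the arm can enter.

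A reader might go further than the documents allow, in four ways.

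- *That evaluators were deliberately left unmasked, and that masking costs nothing.* The text discloses awareness but gives no reason, and masking needs a data-handling step.
- *That the verdict turns on one or two patients.* No event counts are reported. Starting the example at 9 v 8 events with Newcombe puts the trial one step from the boundary; at the planned equal counts the distance is 2 to 4 events, depending on method and level.
- *That 30-day events can sway the verdict.* They are secondary and do not enter the decision rule. All-cause death leaves almost nothing to judge; only need for dialysis is partly a judgement.
- *That results were tilted toward bolus.* Nothing in the documents shows misclassification or its direction.

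It is also right that the plan should not now say that evaluation was masked. Enrolment is reported as ended on 26 March 2025 and 257 patients as analysed, so such wording would misreport the conduct.

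**Conclusion.** The point stands in limited form. Evaluators knew the arm, no reason is given, and the primary outcome could have been classified without it at little cost. The remaining risk lies in the choice of baseline, the choice of sample and the pursuit of non-returners, not in reading the threshold.

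The size is modest but not negligible. A few bolus events separate the planned result from failure, and losing two of them at the margin raises the false non-inferiority rate by a factor of about 2.7 (8.2/3.0 for Wald, 6.8/2.5 for Newcombe). These figures rest on the 128/129 split, the two-sided 95% interval and the planned control rate of 6.2%. They show what a few differential choices could do, not that any occurred. The change is advisable, with medium confidence.

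**What to change.** Keep the statement that the trial was conducted unblinded, because it is true. Then, with existing staff:

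1. Before re-deriving anything, write down one formula for the CA-AKI flag: the last creatinine before any study fluid as baseline, and one fixed rule for the 48-72 h sample (for example the scheduled return sample), identical in both arms. Taking the highest value in the window is less suitable, because it would count more events in patients sampled more often.
2. Apply it to a laboratory export that does not contain the arm.
3. Lock the flag, then merge the allocation, and base the non-inferiority analysis on the locked flag.
4. Report every patient whose status changes, and the number without an in-window sample, by arm.
5. If any follow-up remains, make reminders and 30-day contacts from a list without the arm, using a fixed script.

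The cost is an export, a merge step and a short paragraph of text; N is unchanged and no extra assessor is needed. Two limits remain. The re-derivation cannot repair uneven pursuit of non-returners that has already happened, although the counts in step 4 would help to reveal it. And patients may disclose their arm at the 30-day contact.

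### The trial is sized at one-sided alpha 0.05 but judged by a 95% CI (one-sided 0.025), so it does not have its stated 80% power

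*Combined protocol and SAP*

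**What the plan says.** Two adjacent parts of the combined protocol and SAP set the level of the primary non-inferiority test.

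- **Statistical Analysis.** CA-AKI incidence is compared by risk differences with 95% confidence intervals. The decision rule is that "the protocol was considered non-inferior if the upper bound of the 95% CI was below this margin". The next sentence adds: "All other statistical tests were two-sided, and statistical significance was set at" p < 0.05.
- **Power Calculation.** "A one-tailed hypothesis was established, with a Type I error rate (α) of 0.05", with power 0.80, an anticipated CA-AKI incidence of 6.2% under conventional prophylaxis, a margin of 8% and 15% dropout. This gives 133 per group, 266 in total. The section closes by reporting 257 patients analysed and describing the sample size as adequate: "While 113 individuals in the bolus and continuous prophylaxis groups sufficed for the study".

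The document does not say that the 95% interval is one-sided, mentions no 90% interval, and does not name the interval method.

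**The concern.** Comparing an upper confidence limit with a margin is a one-sided test whose level is set by the interval. The upper limit of a two-sided 95% interval tests at 0.025. A one-sided 0.05 test corresponds to the upper limit of a two-sided 90% interval, or equivalently a one-sided 95% bound. If the decision uses the ordinary 95% interval, the trial was sized for an easier test than the one it applies.

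Two things are at stake. The stated power and the closing claim of adequacy may be wrong. And the only criterion for the trial's main conclusion would be open to two readings, which can disagree on the same data.

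**Working it through.** **Inputs.** From Power Calculation: control incidence 6.2%, margin 8%, one-sided alpha 0.05, power 0.80, dropout 15%, 113 per group before dropout, 257 analysed. From Study Enrollment: 1:1 allocation. Assumptions: the true incidence is also 6.2% under bolus hydration, and the margin is in absolute percentage points (the exact reproduction below supports both). The 257 are taken to split 128/129, because the split is not given.

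**Step 1: reproduce the plan's figure.** Per group,

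n = (z₁₋α + z₀.₈₀)² × 2 × 0.062 × 0.938 / 0.08²

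At one-sided 0.05: (1.645 + 0.842)² = 6.183, and 6.183 × 0.116312 / 0.0064 = 112.4, so 113. Dropout: 113 / 0.85 = 132.9, so 133 per group and 266 in total. All three figures match the plan.

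**Step 2: the same formula at the level of the written rule.** At one-sided 0.025: (1.960 + 0.842)² = 7.849, and 7.849 × 0.116312 / 0.0064 = 142.6, so 143 per group (286 evaluable). With dropout: 143 / 0.85 = 168.2, so 169 per group and 338 in total.

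**Step 3: power at the sizes the plan mentions.** Power = Φ(0.08 / SE − z₁₋α), with SE = √[0.062 × 0.938 × (1/n₁ + 1/n₂)]. For 113 per group, SE = 0.03208 and 0.08 / SE = 2.494. Power is then Φ(2.494 − 1.645) = 80.2% at 0.05, and Φ(2.494 − 1.960) = 70.3% at 0.025.

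| Patients per group | One-sided 0.05 | One-sided 0.025 (95% CI rule) |
|---|---|---|
| 113 / 113 | 80.2% | 70.3% |
| 128 / 129 (257 analysed) | 84.5% | 75.8% |
| 133 / 133 (266 planned) | 85.6% | 77.2% |
| 143 / 143 | 87.7% | 80.1% |

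**Step 4: exact check.** Summing binomial probabilities over all possible tables for the two-sided 95% rule gives:

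- Wald interval: 70.2% at 113/113, 76.0% at 128/129, 77.6% at 133/133.
- Newcombe interval: 65.5%, 69.8% and 72.6%.
- Miettinen-Nurminen score interval: 69.7% at 128/129.

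No method reaches 80% at any of these sizes. Some of the gap between 76% and 70% comes from the interval method and not from alpha: at 128/129 and one-sided 0.05, exact power is 83.9% (Wald), 81.6% (Newcombe) and 80.7% (score).

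**Step 5: can the verdict change?** Take an invented result of 11/128 bolus and 8/129 continuous. The risk difference is 0.0859 − 0.0620 = 0.0239, with Wald SE 0.0326. The 90% upper limit is 0.0239 + 1.645 × 0.0326 = 7.8 points, which passes. The 95% upper limit is 0.0239 + 1.960 × 0.0326 = 8.8 points, which fails. The table is specific to the Wald interval; the score interval fails it at both levels. Across all tables under the planning assumptions at 257, the two readings disagree with probability 83.9 − 76.0 = about 8 points (Wald) or 80.7 − 69.7 = 11 points (score).

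**The case against.** The strongest reply is that the plan meant a one-sided 95% bound. The only alpha stated for the non-inferiority hypothesis is one-tailed 0.05, and the remark that all *other* tests were two-sided marks this test as the one-sided exception. On that reading power is 80.2% at 113 per group and 84.5% at 257, and the closing claims are true.

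That reading is possible but unstated. The remark about other tests is equally true when the upper limit of a two-sided 95% interval is compared with a margin, so it does not settle the level. The interval in the decision rule follows directly from the 95% intervals reported for the risk differences, which an analyst would take as two-sided. If both readings are open, the primary criterion is undefined, and that itself needs correcting.

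Other points on that side stand:

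- The sample-size arithmetic is right for its own alpha. The fault is the mismatch.
- The 95% rule is the stricter one. A result that passes it also passes at one-sided 0.05, so type I error is not inflated and a positive finding under it is not undermined.
- Enrolment closed on 26 March 2025, so no sizing decision can change.
- The flip example is constructed, and disagreement between the readings is likely only about one time in ten.

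These limit the consequences. They do not make the stated power or the adequacy claim correct under the written rule.

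**Conclusion.** The concern holds. Under the decision rule as written, with the 95% interval in its ordinary two-sided sense, the design falls short of 80% power by about 10 points at 113 per group and about 4 points at the 257 analysed. With a Newcombe or score interval the shortfall at 257 is about 10 points. Reaching 80% by the plan's own formula would have taken 30 more evaluable patients per group than the 113 said to be enough (143 − 113).

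These figures rest on 6.2% in both arms, an absolute 8-point margin and a near-equal split of the 257. The conclusion would change only if a one-sided 95% bound had been pre-specified, and the document does not say that it was.

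**What to change.** Make the two sections state the same level. No patients need to be added.

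**Preferred.**
- In Statistical Analysis, say that the interval is two-sided 95%, that comparing its upper limit with the margin is a test at one-sided alpha 0.025, and which interval method is used.
- In Power Calculation, say that the original calculation used one-sided 0.05, that the decision rule would have needed 143 evaluable per group (169 with 15% dropout), and that planning-assumption power under the rule is about 70% at 113 per group and about 76% at 257 (about 70% with a Newcombe or score interval).
- Delete the statement that 113 per group was enough and the claim of adequacy.

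**Alternative, only if one-sided 0.05 was truly the pre-specified decision level.** State the rule as the upper limit of the two-sided 90% interval, state the 5% one-sided type I error, and still report the 95% interval. Adopting this without evidence of pre-specification would loosen the criterion after enrolment closed.

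The cost is a few sentences and a less favourable power statement.
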